3.1. Description of Study Design

This is a multi-center, open label pilot study to assess the safety and determine the feasibility of cockroach nasal allergen challenge (NAC) in children with asthma. This pilot study will occur in two phases. Phase 1 will enroll 10 cockroach sensitive adults with asthma who will undergo a nasal allergen challenge with increasing doses of cockroach allergen. This phase will consist of two parts, Phase 1a and Phase 1b. In Phase 1a, the cockroach sensitive adults will undergo the initial NAC. In Phase 1b, the adult participants will undergo a repeat challenge 30-365 days after the Phase 1a NAC. The purpose of Phase 1b is to assess reproducibility of the NAC with cockroach allergen in a population with asthma. Phase 2 will enroll 25 cockroach sensitive children with asthma who will undergo a NAC with increasing doses of cockroach allergen. Progressing to Phase 2 will not be dependent upon the results of Phase 1b, and Phase 2 will proceed immediately after the completion of Phase 1a. After the completion of Phase 1a, the primary outcome data (positive response to NAC, defined as TNSS \geq 8 out of 12 or a sneezing score of 3) for the participants in Phase 1a will be reviewed to determine the optimal dose range to be used in Phase 2. Considerations for choosing the most appropriate dose range will include tolerability and the aim of eliciting a threshold of nasal symptoms. The investigators planned to use the results of the primary outcome analysis (Section 13.4.2) to determine the optimal dose to be used in Phase 2, with the combination of the optimal dose, one dose above, and 2 doses below the optimal dose to be selected as the four doses to be used in Phase 2. However, an optimal dose was not determined in Phase 1a. It was noted that no adult reacted to the first dose of allergen (challenge dose 2).

Phase 2 will enroll 25 cockroach sensitive children with asthma, ages 8-14 years, who will undergo a nasal allergen challenge with all 8 allergen doses used in Phase 1a in at least the first 5 participants to ensure a similar pattern of response. If none of these 5 children react to the first dose of allergen (challenge dose 2), then that dose will be dropped from subsequent challenges. The threshold for a positive response to the NAC in Phase 2 will be defined as a TNSS \geq 6; the sneezing score of 3 will remain the same.

[figure not shown]

Figure 3.1 Cockroach Nasal Allergen Challenge Study Design

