4.3. Exclusion Criteria

Individuals who meet any of these criteria are not eligible for enrollment as study participants in Phase 1a and Phase 2:

1. Are pregnant or lactating. Post-menarcheal females must be abstinent or use a medically acceptable birth control method throughout the study (e.g. oral, subcutaneous, mechanical, or surgical contraception).
2. Cannot perform spirometry at Screening.
3. Have an asthma severity classification at Recruitment of severe persistent, using the NAEPP classification, as evidenced by at least one of the following:
 - a. Require a dose of greater than 500 mcg of fluticasone per day or the equivalent of another inhaled corticosteroid.
 - b. Have received more than 2 courses of oral or parenteral corticosteroids within the last 12 months or one course within the last 3 months.
 - c. Have been treated with depot corticosteroids within the last 12 months.
 - d. Have been hospitalized for asthma within the 12 months prior to recruitment.
 - e. Have had an emergency room visit for asthma within the 3 months prior to recruitment.
 - f. Have had a life-threatening asthma exacerbation that required intubation, mechanical ventilation, or that resulted in a hypoxic seizure within 2 years prior to recruitment.
4. Have nasal polyps or other major structural abnormalities in their nasal cavities as assessed by anterior rhinoscopy.
5. Have active rhinitis symptoms prior to the nasal allergen challenge, defined as a Baseline TNSS >3 , with no individual symptom score >1 .

6. Do not have access to a phone (needed for scheduling appointments).
7. Have received allergen immunotherapy (SLIT or SCIT) in the last 12 months prior to recruitment or who plan to initiate or resume allergen immunotherapy during the study.
8. Have previously been treated with anti-IgE therapy in the 12 months prior to recruitment.
9. Are currently receiving oral or nasal antihistamines, nasal corticosteroids, nasal decongestants, nasal anticholinergics or cromolyn, which cannot be suspended for the required washout periods prior to skin prick testing and the nasal allergen challenge.
10. Have received an investigational drug in the 30 days prior to recruitment or who plan to use an investigational drug during the study.

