6.1.2. Dosage, Preparation, and Administration

Dilutions of the German cockroach allergenic extract needed for NAC dose escalation will be prepared by the site research pharmacy.

Participants will receive escalating doses of glycerinated German cockroach allergenic extract administered via the intranasal route. Each dose will be administered as a nasal spray with the use of a nasal drug delivery system (LMA/Teleflex, San Diego, CA), which delivers 0.1 mL per activation (spray). One spray will be delivered in each nostril for a total delivered volume of 0.2 mL. Nine doses will be given. Dose 1 will be a diluent control. Doses 2 through 9 will have a Bla g 1 dose range of approximately 0.002 mcg to 5 mcg.

All 8 allergen doses will be used in the first 5 children in Phase 2 to ensure a similar response pattern to that seen in the adults. If, like in the adults in Phase 1, none of these 5 children react to the first allergen dose, this dose will be dropped from the subsequent challenges. The threshold for a positive response to the NAC in Phase 2 will be defined as a TNSS ≥ 6 ; the sneezing score of 3 will remain the same.

The proposed NAC dose escalation for Phase 2 was reviewed and approved by the NIAID Allergy and Asthma DSMB.

Complete details of the dilutions can be found in the MOP for Protocol ICAC-27, which is based on the DAIT Pharmacy manual.

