11. Nasal allergen challenge (NAC) - increasing doses of allergen in defined time intervals (every 20 minutes) up to a specified maximum dose or symptom level, will be given as described in an accompanying MOP for Protocol ICAC-27. Briefly, one spray (100mcL) of diluent or diluted allergen solution is applied to each of the participant's nostrils using a nasal drug delivery system while the participant breath-holds at TLC. After the dose is delivered, the participant is asked to exhale through the nose and then to avoid sniffing or swallowing in the immediate 1 minute after application. In Phase 1, the challenge will begin with a 0 mcg/ml (negative control – 50% glycerin, 50% COCAS with 0.2% phenol) dose followed by up to 8 doses of increasing concentration, until the participant reaches a TNSS score of 8 or more, has a sneezing score of 3 or their symptoms become intolerable. In Phase 2, the challenge will begin with a 0mcg/ml (diluent control) dose followed by a number of doses of increasing concentration, until the participant reaches a TNSS score of ≥ 6 , has a sneezing score of 3 or their symptoms become intolerable. All 8 allergen doses will be used in the first 5 children in Phase 2 to ensure a similar response pattern to that seen in the adults. If, like in Phase 1 in adults, none of these 5 children react to the first allergen dose, this dose will be dropped from the subsequent challenges. Nasal secretions will be collected for approximately 10 minutes immediately following administration of each diluent and allergen dose and a nasal rinse (two 100mcL sprays of isotonic saline solution per nostril) will be performed at 10 minutes, as described above. The fluids from each rinse will be mixed with the nasal secretions collected during the preceding 10 minutes and processed for analysis as specified in the MOP for Protocol ICAC-27. Collection of other outcomes will begin 10 minutes after each diluent or allergen dose is administered. If a participant begins exhibiting asthma symptoms during the NAC, or the PEF is reduced by more than 20% from baseline, the challenge will be suspended, and the participant will be evaluated by the study clinician. If it is determined treatment is needed based on clinical judgment, then the challenge will not be continued. In the absence of an immediate need for treatment, spirometry will be performed to confirm a change in lung function. If the FEV1 is $< 85\%$ of baseline value, the challenge will be stopped. If spirometry is performed because of a low PEF and the FEV1 is $\geq 85\%$ of baseline value, the challenge can continue at the clinician's discretion.

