13.4.2 Primary Analysis of Primary Outcomes

The first primary objective of this analysis is to estimate a probability of positive response at each dose, defined as reaching a sneezing score of 3 or a TNSS of ≥ 8 in Phase 1 or a TNSS of ≥ 6 in Phase 2. The probability of reaching a positive response will be estimated using the percentage of responses in subjects at each of the 9 doses. Although a participant will stop receiving doses once they have reached a sneezing score of 3 or a TNSS of ≥ 8 in Phase 1 or a TNSS of ≥ 6 in Phase 2, it is assumed that they would continue to respond for the remaining doses. Therefore, if 7 people respond prior to Dose 5, 3 will be tested at Dose 5, and the proportion presented for Dose 5 would be $(7 + \# \text{ responders at Dose 5})/10$. Associated exact 95% confidence intervals will be estimated using the Clopper-Pearson method.

The second primary objective of this analysis is to assess if intranasal delivery of cockroach allergen via a nasal allergen challenge is safe. This will be done by determining the rate of related adverse events and serious adverse events in the course of treatment. Frequency of AEs and SAEs will be tabulated by event, organ, seriousness, severity, and treatment relatedness.

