7.1.4 Computation of the Primary Efficacy Outcomes

In adults in the Phase 1a cohort, a positive response at each dose will be defined as TNSS ≥ 8 or a sneezing score of 3. In children in the Phase 2 cohort, a positive response at each dose will be defined as TNSS ≥ 6 or a sneezing score of 3.

The probability of reaching a positive response will be estimated by calculating the percentage of responses in subjects at each of the 9 doses. Although a participant will stop receiving doses once they have a positive response, it is assumed that they would continue to respond for the remaining doses. For example, if 7 of the 10 participants in Phase 1 respond prior to Dose 5, 3 will be challenged with Dose 5, and the proportion presented for Dose 5 would be $(7 + \# \text{ responders at Dose 5})/10$.

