7.2.2 Secondary Efficacy Outcome 2 – Maximum TNSS Score Over All Doses

The maximum TNSS score over all doses received in each of the Phase 1a and Phase 2 cohorts will be summarized across participants and examined with 95% confidence intervals and boxplots. Maximum TNSS score will additionally be listed for each subject.

7.2.3 Secondary Efficacy Outcomes 3-8 – Change from Baseline in TNSS, PNIF, PEF, VAS, Tryptase in Nasal Secretions, and Albumin in Nasal Secretions.

For each of the six variables TNSS, PNIF, PEF, VAS, tryptase, and albumin, the baseline score will be defined as the value obtained at the post-rinse baseline assessment in the challenge. The post-baseline score will be the one associated with the highest dose received in the challenge. Change from baseline will then be computed as post-baseline minus baseline. Whether change is different from zero will be assessed for each of these variables for each of the Phase 1a and Phase 2 cohorts using 95% confidence intervals and boxplots. Values for each of the six variables at each dose will be listed and displayed graphically for each subject. TNSS, sneeze score, and PNIF as well as TNSS, sneeze score, and VAS will be overlaid together graphically for each subject.

Tryptase and albumin will be transformed using a natural logarithm prior to analysis, as necessary. The lowest and highest detectable values will be substituted for values below and above the measureable thresholds, respectively. The number and percent of values that are above or below detectable thresholds will be tabulated for each variable and phase using frequency tables.

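### The carry-forward rule counts a participant who responds to diluent as a responder at every allergen dose, although that participant never receives allergen

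*SAP*

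**What the plan says.** Protocol 6.1.2 sets the sequence: "Nine doses will be given. Dose 1 will be a diluent control". Doses 2 to 9 are allergen. Protocol 8.3 applies the stopping threshold from diluent onward. For children it reads: "the challenge will begin with a 0mcg/ml (diluent control) dose followed by a number of doses of increasing concentration, until the participant reaches". The end point there is a TNSS of at least 6, a sneezing score of 3 or intolerable symptoms. Phase 1 has the same structure with a TNSS threshold of 8.

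The first primary analysis covers the whole sequence. Protocol 13.4.2 states: "The probability of reaching a positive response will be estimated using the percentage of responses in subjects at each of the 9 doses". SAP 7.1.4 likewise takes the "percentage of responses in subjects at each of the 9 doses" and adds the carry-forward assumption: "a participant will stop receiving doses once they have a positive response, it is assumed that they would continue to respond for the remaining doses". The example in both documents adds all earlier responders to those at dose 5 and divides by the full Phase 1 cohort of 10. SAP 7.1.3 gives the target as prevalence of a positive challenge at each cockroach allergen dose.

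The analysis population is everyone who received the initial dose (protocol 13.4.1, SAP 4), so a participant who stops at diluent stays in.

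For Phase 2, protocol 3.1 adds a drop rule: "If none of these 5 children react to the first dose of allergen (challenge dose 2), then that dose will be dropped from subsequent challenges". Sections 6.1.2 and 8.3 repeat it.

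**The concern.** Carrying a response from one allergen dose to a higher one rests on a sensible monotonicity assumption. Carrying it from diluent to allergen does not, because the participant has shown a reaction to the vehicle or the procedure and has had no allergen. Read literally, the rule still makes this participant a responder at all eight allergen doses.

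Nothing else in the plan corrects this. Positivity is an absolute score, without subtraction of the diluent score. For the change-from-baseline outcomes in SAP 7.2.3, "the baseline score will be defined as the value obtained at the post-rinse baseline assessment in the challenge", so diluent is not the reference there either. The rhinitis exclusion in protocol 4.3 ("Have active rhinitis symptoms prior to the nasal allergen challenge, defined as a Baseline TNSS" above 3) acts before the challenge, not after diluent. A child may enter at a TNSS of 3 and needs a rise of 6 − 3 = 3 points to be positive. Five sneezes alone also suffice.

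At stake are the percentages and exact intervals of the first primary outcome. The effect is largest at the low doses, where few participants truly respond and where the lower end of the dose range is judged. The drop rule counts observed reactions to dose 2 and the estimator counts carried-forward ones, so the two can disagree about the same dose.

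**Working it through.** **Inputs from the documents.** Nine doses, dose 1 diluent (protocol 6.1.2); 10 adults and 25 children (protocol 13.6); carry-forward and Clopper-Pearson 95% intervals (SAP 7.1.4 and 7.1.5); drop rule on the first five children (protocol 3.1). The diluent response rate q is not given, so 2%, 5% and 10% are assumed.

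**The plan's own figures.** Clopper-Pearson limits for n = 10 agree with all 11 rows of the table in protocol 13.6, for example 0/10: 0 to 0.31; 5/10: 0.19 to 0.81; 10/10: 0.69 to 1.00.

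**How the rule counts.** The count at dose d is the number of participants whose first positive dose is d or lower. Take five children with first positive doses 1, 5, 6, 7 and none. The counts at doses 1 to 9 are 1, 1, 1, 1, 2, 3, 4, 4, 4. The diluent responder appears at every allergen dose.

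**Size per diluent responder.** Let r be the number of other participants counted positive at a dose.
- Phase 2: reported (1 + r)/25, against r/24 among those not stopped at diluent. The difference is (24 − r)/600, which is 4 points at r = 0, 2 points at r = 12 and 0 at r = 24.
- Phase 1: (1 + r)/10 − r/9 = (9 − r)/90, which is 10 points at r = 0 and 0 at r = 9.

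**Expected size.** With true allergen response p among the rest, the reported prevalence has expectation q + (1 − q)p, an excess of q(1 − p). At q = 5% this is 5 points at p = 0 and 2.5 points at p = 50%.

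**Chance that it arises,** 1 − (1 − q)^n:

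| Assumed q | n = 5 | n = 10 | n = 25 |
|---|---|---|---|
| 2% | 10% | 18% | 40% |
| 5% | 23% | 40% | 72% |
| 10% | 41% | 65% | 93% |

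**Drop rule.** Suppose one of the first five children responds to diluent and the other four do not react to dose 2. No child reacts to dose 2, so it is dropped. The dose 2 estimate is then:

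| Counting | Estimate | 95% interval |
|---|---|---|
| Carry-forward, children scheduled for dose 2 | 1/5 = 20% | 0.5% to 72% |
| Carry-forward, whole cohort as in the SAP example | 1/25 = 4% | 0.1% to 20% |
| Only children given dose 2 | 0/4 = 0% | 0% to 60% |

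The plan does not say which denominator applies to a dropped dose. Under either carry-forward reading, a dose discarded as unreactive is reported as non-zero.

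**The case against.** The strongest reply is that SAP 7.1.4 estimates the probability of reaching the threshold at each dose, not the part due to allergen. Allergen is given in diluent, so a child who reacts to the vehicle might also cross the threshold on vehicle plus allergen, and q + (1 − q)p could then be the intended quantity. This has some force and is why a sensitivity analysis should keep the present counting. It does not settle the matter: SAP 7.1.3 names allergen doses as the target, and the carried-forward response is assumed without any allergen having been given.

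Planned output would expose the problem. SAP 7.1.5 gives dose 1 its own estimate, tabulates threshold attainment by dose and lists scores by subject, so any diluent responder could be identified. That stands, but the reported percentages and intervals at doses 2 to 9 would remain uncorrected.

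Three further limits stand. Phase 1a is complete in this protocol version, so the sponsor can already tell whether any adult responded to diluent; the report in protocol 3.1 that no adult reacted to dose 2 does not answer that. The manual of procedures governs challenge conduct, was not available, and may hold a rule. For the drop decision itself, 0/4 in place of 0/5 moves the upper limit only from 52% to 60%.

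Two stronger readings are tempting. One is that dose 2 would be reported as 20%. That needs a denominator of five, which the plan does not state, and protocol 3.1 allows more than five children on the full sequence. The other is that carry-forward could falsely show a response in most children. Protocol 2.2 speaks of most participants, but the plan contains no 50% decision rule. The chance of crossing 50% only through carry-forward also depends heavily on p. For q = 2%, 5% and 10% it is 6%, 13% and 24% at p = 45%, but 1%, 3% and 7% at p = 30%, and 1%, 1% and 2% at p = 70%. These figures are illustration only.

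**Conclusion.** The point holds as a defect in a stated rule of the primary analysis. As written, a participant who responds to diluent is counted as an allergen responder at doses 2 to 9, against the target in SAP 7.1.3. The size is at most 4 points per such participant at each allergen dose in Phase 2 and at most 10 in Phase 1, shrinking as true response rises. It is nil if nobody responds to diluent.

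The documents do not show that any diluent response occurred, and every rate used above is assumed. The conclusion also presumes that no rule for diluent responders exists in the manual of procedures; if one does, the SAP should state it. This is a descriptive pilot without a hypothesis test, so the consequence is a misstated estimate and interval, not a false test result. A correction is worthwhile because it takes only a few sentences.

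**What to change.** **SAP 7.1.4 and protocol 13.4.2.** Limit carry-forward to responses at allergen doses (2 to 9). Report a participant who is positive at dose 1 in the dose 1 row, and leave that participant out of the numerator and denominator at doses 2 to 9. Add two sensitivity analyses: diluent responders counted as non-responders at doses 2 to 9, and counted as responders, as now written. Show the number challenged at each dose. For a dose dropped in Phase 2, use only the children whose sequence included it.

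**Protocol 13.4.1 and SAP 4.** The protocol requires every analysis to use the Safety Population, so add the matching exception for the dose-response estimates. Keep diluent responders in that population for safety.

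**Protocol 3.1, 6.1.2 and 8.3.** State that the drop rule is applied once at least five children have been challenged at dose 2. This fits the existing allowance in 3.1 for more than five children on the full sequence.

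**Cost.** A few sentences, with no added sample size or visits. The denominator at allergen doses falls by one per diluent responder (25 to 24 with one). One more child may receive dose 2 for each of the first five who stops at diluent. If children who react to diluent are also the more allergen-reactive ones, leaving them out could lower the estimate somewhat; the two sensitivity analyses bracket this.

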11.3. Participant Replacement

Participants who withdraw or are withdrawn will not be replaced if they have received at least one dose of the investigational product.

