13.4 Analysis Plan

13.4.1 Analysis Populations

The study population consists of adults aged 18 through 55 years (phase 1) and children ages 8 through 14 years (phase 2) who have a history of asthma and are German cockroach sensitive. The study will examine the safety of the administration of non-standardized German cockroach extract delivered intranasally. This is a phase I safety pilot study with no efficacy measures; thus, only one analysis population, the safety population, will be defined for this study. The safety population will include all study participants who receive the initial dose during the Challenge Visit. All statistical analyses will be performed on the Safety Population.

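### The full-cohort prevalence formula counts participants who were never given a dose, and had not responded, as observed non-responders at that dose

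*SAP*

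**What the plan says.** SAP 7.1.4 defines the first primary outcome by "calculating the percentage of responses in subjects at each of the 9 doses", that is, the diluent and eight allergen doses. Dosing stops after a positive response, and for those participants "it is assumed that they would continue to respond for the remaining doses". In the worked example seven of ten adults have responded before Dose 5: "3 will be challenged with Dose 5, and the proportion presented for Dose 5 would be" seven plus the new responders, over ten. Protocol 13.4.2 gives the same rule. SAP 7.1.5 attaches Clopper-Pearson intervals in both cohorts.

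Protocol 13.4.1 says "All statistical analyses will be performed on the Safety Population", which is everyone given the initial dose at the Challenge Visit. On replacement, protocol 11.3 says: "Participants who withdraw or are withdrawn will not be replaced if they have received at least one dose" of the product.

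The design has two other ways for a participant to miss a dose.

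- **Dropped dose.** Protocol 3.1 gives all eight allergen doses to at least the first 5 children. If none of them reacts to challenge dose 2, "then that dose will be dropped from subsequent challenges". Protocol 6.1.2 and 8.3 repeat this.
- **Stop without a positive response.** Under protocol 8.3 dosing continues until the participant reaches the TNSS threshold, "has a sneezing score of 3 or their symptoms become intolerable". Sections 5.1.1 and 8.3 also end the challenge for a need for treatment or an FEV1 below 85% of baseline. Section 11.2 lists inability to tolerate the challenge before the threshold as a reason for withdrawal.

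SAP 7.2 acknowledges truncated data, but only after a positive response. The SAP's one sentence on missing data (8.1) concerns safety.

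**The concern.** The example obtains its three challenged adults as 10 − 7. That holds only if nobody has left the escalation for any reason other than responding. Someone who was not given a dose and had not responded adds nothing to the numerator but stays in the denominator, so the table shows them as if they had been tested and found negative.

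The first primary objective is to find doses that reach the symptom threshold in most participants, and protocol 1.1 says the results will inform whether and how the challenge is used in a later immunotherapy trial. At a dropped dose, absence of data would look like good evidence of no response. At higher doses, an early stop can only pull the printed proportion down relative to what continued dosing would have shown.

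**Working it through.** **The plan's own figures.** Protocol 13.6 tabulates exact 95% intervals for 0 to 10 responses out of 10. Clopper-Pearson limits from beta quantiles reproduce all 11 rows within rounding: 0/10 gives 0 to 0.3085 (stated 0.31), and 7/10 gives 0.3475 to 0.9333 (stated 0.35, 0.93).

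**Dropped dose.** Inputs: 25 children (protocol 13.6), at least 5 given challenge dose 2 (3.1), none of them reacting, so up to 25 − 5 = 20 undosed. With zero responses the upper limit is 1 − 0.025^(1/n).

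- Full cohort, 0/25: 1 − 0.025^(1/25) = 0.137.
- Children dosed, 0/5: 1 − 0.025^(1/5) = 0.522.

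The second limit is about 3.8 times the first (0.522/0.137). If the true rate were 20%, 0 of 5 would occur with probability 0.8^5 = 0.33.

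The plan's persistence assumption narrows this if it is also applied backwards. A child who would respond at dose 2 would also respond at dose 3, so a child negative at dose 3 must be negative at dose 2. Only the k undosed children first positive at dose 3 remain unknown, and prevalence at dose 2 lies between 0/25 and k/25, plus any diluent responders in both bounds. The documents do not give k. For illustration, k = 2 gives 0 to 8% and k = 4 gives 0 to 16%.

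**Early stops.** With x responders, s participants stopped without a response, and N in the cohort, the plan prints x/N. The data allow x/N (none would have responded) to (x + s)/N (all would have). Each stop therefore contributes up to 1/10 = 10 points in adults or 1/25 = 4 points in children. The values of x and s below are assumptions.

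| Case | Plan prints | Bounds | Stops excluded |
|---|---|---|---|
| Adults, x = 6, s = 2 | 6/10 = 60% | 60% to 80% | 6/8 = 75% |
| Adults, x = 8, s = 1 | 8/10 = 80% | 80% to 90% | 8/9 = 88.9% |
| Children, x = 20, s = 1 | 20/25 = 80% | 80% to 84% | 20/24 = 83.3% |
| Children, x = 20, s = 3 | 20/25 = 80% | 80% to 92% | 20/22 = 90.9% |

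The last column shows why exclusion is not the remedy. Earlier responders stay in while stopped non-responders leave, so the proportion rises by construction.

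**The case against.** **The full denominator can be defended.** SAP 7.1.4 speaks of reaching a positive response. Someone stopped for intolerance or lung function did not reach it, so cumulative responders over all who started answers a sensible feasibility question. This stands. The figure is biased down only if the target is response had dosing continued, and the plan does not say which target it means. Carrying earlier responders forward to doses they never received leans toward the second.

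**The Phase 2 denominator is not written down.** Ten appears in a Phase 1 example; 25 follows from the safety-population rule. The phrase about subjects at each dose could be read as those tested. This stands in part: 25 is an inference, but the worked example contradicts the tested-only reading.

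**The effect may be small or absent.** The drop is conditional, 20 is a maximum, and there may be no early stops. Phase 1a had already informed Phase 2 dosing, so the adult figures cannot change that decision. The 60% to 80% range lies inside the plan's own interval for 6/10 (0.26 to 0.88). All of this is fair and limits the severity, although sampling error and unobserved doses are separate uncertainties and the interval conveys only the first.

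**Existing outputs expose the gaps.** SAP 7.1.5 lists TNSS and sneeze score by dose for each subject, and SAP 5.1 and 8.2 report reasons for termination and adverse events leading to discontinuation. These let a reader find the missing doses but leave the headline estimate and interval unchanged.

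A reader might also infer that those stopped early are the most sensitive participants. The documents do not support this. They stopped without meeting the nasal threshold, an FEV1 fall is a lower-airway event, and protocol 1.1 itself says nasal outcomes do not match lower-airway ones.

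**Conclusion.** The point holds and should be corrected, though it does not invalidate the primary analysis. The stated formula handles stopping after a response and has no rule for anyone else who misses a dose; followed literally, it scores them as tested and negative.

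At a dropped first allergen dose the fault is false precision: an upper limit of 13.7% instead of 52.2% from five children dosed. This assumes a denominator of 25, exactly five children dosed, none reacting, and no diluent responders. The 52.2% is itself wide if the persistence assumption is accepted backwards, but the plan does not make that argument. For early stops, later doses may be understated by up to 10 points per adult or 4 per child, only if the target is response had dosing continued, and in a number the documents do not give.

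It would go too far to conclude that the full-cohort proportion is wrong in itself, or that 20 children will certainly miss the dose. The first depends on an unstated target, the second on a conditional rule.

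**What to change.** In SAP 7.1.4, with matching text in protocol 13.4.2:

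1. Keep the full-cohort proportion, label it as the proportion reaching threshold during the escalation, and state the Phase 2 denominator.
2. Show the number actually dosed beside each estimate.
3. For participants stopped without a positive response, give lower and upper bounds at later doses (none or all would have responded), with the dose and reason for stopping. Do not simply exclude them.
4. If challenge dose 2 is dropped, report the estimate and exact interval among the children challenged before it was dropped. Alternatively, state that persistence is applied backwards and give bounds of 0/25 to k/25, adding any diluent responders to both.

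The cost is a few sentences, one table column and a pair of bounds; trial conduct and clinical rules are untouched. The price in reporting is a wider interval (or a range) at the dropped dose, and a range instead of one figure where early stops occur.
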